- Check concomitant therapy and adverse events
- Record vital signs
- Drug return / accountability and re-dispensation of unused kits/blister
- Diary collected and checked
- *Photographic documentation only for a subgroup (see section 5.5.1.4)*
- Urinalysis (see section 5.5.2)
- Collection of samples for determination of laboratory parameters (hematological status, clinical chemistry, urinalysis, see section 5.5.2)
- PASI (see section 5.5.1.1)

- PGA (see section 5.5.1.2)
- BSA (see section 5.5.1.3)
- Dispensing of IMP and diary

Trial Day 84 (week 12, visit 5) (EoT)

- Check concomitant therapy and adverse events
- Physical examination (see section 5.5.5)
- Record vital signs (see section 5.5.3)
- Urine pregnancy test and urinalysis (see section 5.5.2)
- *Photographic documentation only for a subgroup (see section 5.5.1.4)*
- Collection of samples for determination of laboratory parameters (hematological status, clinical chemistry, see section 5.5.2)
- *PK samples only for a subgroup (see section 5.5.1.5)*
- Last IMP administration at site for all patients
- Drug return / accountability
- Diary collected and checked
- PASI (see section 5.5.1.1)
- PGA (see section 5.5.1.2)
- BSA (see section 5.5.1.3)

Trial Day 112 (week 16, visit 6, Follow-up) (End of Study, EoS)

- *Photographic documentation only for a subgroup (see section 5.5.1.4)*
- Check concomitant therapy and adverse events
- Physical examination (see section 5.5.5)
- Record vital signs (see section 5.5.3)
- Urinalysis(see section 5.5.2)
- Collection of samples for determination of laboratory parameters (hematological status, clinical chemistry, see section 5.5.2)
- PASI (see section 5.5.1.1)
- PGA (see section 5.5.1.2)
- BSA (see section 5.5.1.3)

The patients must be present at site for approximately 60 minutes on Screening and Day 1, 45 minutes on Day 28 and 56, 60 minutes on Day 84 and 45 minutes on Day 112.

The above mentioned time will be extended for 15 minutes for patients with photographic documentation on each visit.

The above mentioned time will be extended on Day 1 and Day 84 for 120 minutes for patients with PK sampling.

Early Termination Visit

Patients who discontinue early from the trial should, if possible, have an Early Termination Visit. This visit should take place as soon as possible after the patient stops taking IMP. The observations and procedures scheduled for Visit 5 (End of Treatment) should be performed at the Early Termination Visit.

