6.6 Handling of dropouts and missing data

For the evaluation of success rates of the primary efficacy variables PASI and PGA missing PGA assessments and/or any parts of the PASI assessments will be evaluated as failure to achieve improvement. For descriptive analyses of PASI, PGA and BSA the last observation carried forward (LOCF) principle will be applied to impute the missing assessments, up to the Day 84 visit. Follow-up assessments will not be imputed.

Sensitivity of the primary efficacy analyses will be evaluated applying PP analyses.

Handling of missing AE data, will be detailed in the SAP.

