1.3 Modifications from the statistical section in the protocol

Not applicable.

2 Investigational plan

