3.1 Definitions

The following definitions apply:

- Baseline: The latest non-missing observation prior to first treatment with IMP.

Baseline data definition	obtained on/at
Age, race, height, body weight, BMI	Screening
Relevant medical history (last 5 years) including psoriasis history, relevant surgical history (last 5 years) and relevant previous medication (last 6 weeks) including psoriatic treatment taken (last 6 weeks)	Screening
Smoking and alcohol consumption	Screening
Concomitant medication	Day 1
Adverse events	Day 1
Physical examination	Day 1, Screening*
Vital signs (blood pressure, pulse rate)	Day 1, Screening*
Safety laboratory parameters	Day 1, Screening*
PASI, PGA, BSA	Day 1, Screening*

*only in case of missing Day 1 assessment

- Change from baseline = post baseline value – baseline value
- Percent change from baseline = $100 * \text{change from baseline} / \text{baseline value}$
- Last observation carried forward (LOCF): The last observed value (either scheduled or unscheduled) carried forward and used for all directly subsequent and missing scheduled points.
- Current medical conditions – medical conditions ongoing at first dosing.
- Prior therapy: Any medication or therapy taken prior to start of first IMP dosing.
- Concomitant therapy: A medication or therapy ongoing at start of first IMP dosing, or starting after the first IMP dosing.
- Treatment emergent adverse event (TEAE): Adverse event with an onset (or worsening) on or after the time of the first IMP dosing.
- Time to achievement of PASI 50 (75): Day of first visit were PASI 50 (75) is observed.
- Analysis centers: Pooled small centers for analyses, as described in section 3.5.4.

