3.5.1 Missing data

A description of missing data will be provided in the clinical study report.

For the evaluation of success rates of the primary efficacy variables PASI and PGA missing PGA assessments and/or any parts of the PASI assessments will be evaluated as failure to achieve improvement.

For descriptive analyses of PASI, PGA and BSA the last observation carried forward (LOCF) principle will be applied to impute the missing assessments, up to the Day 84 visit. Follow-up assessments will not be imputed.

Sensitivity of the primary efficacy analyses will be evaluated applying PP analyses.

Regarding incomplete recordings for adverse events the following rules apply:

- For start and stop dates no imputation will be applied. If any, start or stop date, is not complete, but required for the classification, i.e. the occurrence of the AE is not explicitly reported as occurring prior first dose (see eCRF), the AE will be considered treatment emergent.
- Missing assessments of severity, intensity and causal relationship to the IMP will be reported as a separate category.

For the determination of the number of years from start of psoriasis to the screening visit missing starting days will be imputed by the first day of month and missing months will be imputed by the first month (January) of the year.

For concomitant therapies (see section 3.2.2.4) incomplete dates will not be imputed. If an incomplete start or stop date does not allow for the classification as prior and/or concomitant therapy - despite of information in eCRF if taken/used prior to first dosing and/or if ongoing at first dosing - the treatment will be reported as prior and as concomitant therapy.

Pharmacokinetic data below LLQ will be replaced as described in 3.4.7.3 for descriptive statistics and for the derivation of $AUC_{(0,t)}$. Missing pre-dose levels will be imputed by zero. Missing intermediate samples, i.e. missing values in between non-missing levels (quantifiable or substituted by LLQ/2) will be imputed by linear interpolation between the last preceding and the next following available value. The last value will be imputed by LLQ/2, if missing.

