Mean ± SD	XX.X ± XX.X	XX.X ± XX.X	XX.X ± XX.X
Median	XX.X	XX.X	XX.X
Min , max	XX.X , XX.X	XX.X , XX.X	XX.X , XX.X
Change from Baseline ¹			
N	XX	XX	XX
Mean ± SD	XX.X ± XX.X	XX.X ± XX.X	XX.X ± XX.X
Median	XX.X	XX.X	XX.X
Min , max	XX.X , XX.X	XX.X , XX.X	XX.X , XX.X
Week 16 / Follow-up			
N	XX	XX	XX
Mean ± SD	XX.X ± XX.X	XX.X ± XX.X	XX.X ± XX.X
Median	XX.X	XX.X	XX.X
Min , max	XX.X , XX.X	XX.X , XX.X	XX.X , XX.X
Change from Baseline ¹			
N	XX	XX	XX
Mean ± SD	XX.X ± XX.X	XX.X ± XX.X	XX.X ± XX.X
Median	XX.X	XX.X	XX.X
Min , max	XX.X , XX.X	XX.X , XX.X	XX.X , XX.X

¹ Baseline: Last observation collected prior to first dose of any IMP, i.e. Day 1 assessment or, if missing, Screening assessment.

Source data: <DATASET> <DATE>
Program: <SAS PROGRAM> <DATE>

Figure 14.1: PASI – Lineplot: Mean values by treatment over time – LOCF (FAS)
Mean values per visit and treatment (visits on x-axis)

Figure 14.2: PASI – Lineplot: Mean change from baseline by treatment over time – LOCF (FAS)
Mean change from baseline per visit and treatment (visits on x-axis)

Table 14.3.3: PASI – PASI 75 responders – LOCF (FAS)
(Part 1 of 2)

PASI 75¹ – LOCF	MP1032 300 mg bid (N = XX)	MP1032 150 mg bid (N = XX)	Placebo bid (N = XX)
Week 4			
N	XX	XX	XX
Responder	XX (XXX.X%)	XX (XXX.X%)	XX (XXX.X%)
Non responder	XX (XXX X%)	XX (XXX X%)	XX (XXX X%)
Comparison vs Placebo ²			
p-value	X.XXX	X.XXX	--
Odds ratio	X.XX	X.XX	--
Confidence interval	X.XX, X.XX	X.XXX	--
Breslow-Day test ³	X.XXX	X.XXX	--
Week 8			
N	XX	XX	XX
Responder	XX (XXX.X%)	XX (XXX.X%)	XX (XXX.X%)
Non-responder	XX (XXX.X%)	XX (XXX.X%)	XX (XXX.X%)
Comparison vs Placebo ²			
p-value	X.XXX	X.XXX	--
Odds ratio	X.XX	X.XX	--
Confidence interval	X.XX, X.XX	X.XXX	--
Breslow-Day test ³	X.XXX	X.XXX	--
Week 12 / EoT			
N	XX	XX	XX
Responder	XX (XXX.X%)	XX (XXX.X%)	XX (XXX.X%)
Non-responder	XX (XXX.X%)	XX (XXX.X%)	XX (XXX.X%)
Comparison vs Placebo ²			
p-value	X.XXX	X.XXX	--
Odds ratio	X.XX	X.XX	--
Confidence interval	X.XX, X.XX	X.XXX	--
Breslow-Day test ³	X.XXX	X.XXX	--

¹ 75% improvement in PASI score

² Cochran-Mantel-Haenszel (CMH) test: p-value for the hypothesis, that all within-stratum odds ratios equal to 1 and estimate of the common odds ratio with 95% confidence interval

³ p-value of Breslow-Day test for the hypothesis that all individual odds-ratios are equal

Source data: <DATASET> <DATE>

Program: <SAS PROGRAM> <DATE>

Table 14.3.3: PASI – PASI 75 responders – LOCF (FAS)
(Part 2 of 2)

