2 – Mild	XX (XXX.X%)	XX (XXX.X%)	XX (XXX.X%)
3 – Mild to moderate	XX (XXX.X%)	XX (XXX.X%)	XX (XXX.X%)
4 – Moderate	XX (XXX.X%)	XX (XXX.X%)	XX (XXX.X%)
5 – Moderate to severe	XX (XXX.X%)	XX (XXX.X%)	XX (XXX.X%)
6 – Severe	XX (XXX.X%)	XX (XXX.X%)	XX (XXX.X%)

Source data: <DATASET> <DATE>
Program: <SAS PROGRAM> <DATE>

Table 14.3.14: PGA – Frequency counts – LOCF (FAS)
(Part 2 of 2)

PGA	MP1032 300 mg bid (N = XX)	MP1032 150 mg bid (N = XX)	Placebo bid (N = XX)
Week 12 / EoT			
N	XX	XX	XX
0 – Clear	XX (XXX.X%)	XX (XXX.X%)	XX (XXX.X%)
1 – Almost clear	XX (XXX.X%)	XX (XXX.X%)	XX (XXX.X%)
2 – Mild	XX (XXX.X%)	XX (XXX.X%)	XX (XXX.X%)
3 – Mild to moderate	XX (XXX.X%)	XX (XXX.X%)	XX (XXX.X%)
4 – Moderate	XX (XXX.X%)	XX (XXX.X%)	XX (XXX.X%)
5 – Moderate to severe	XX (XXX.X%)	XX (XXX.X%)	XX (XXX.X%)
6 – Severe	XX (XXX.X%)	XX (XXX.X%)	XX (XXX.X%)
Week 16 / Follow-up			
N	XX	XX	XX
0 – Clear	XX (XXX.X%)	XX (XXX.X%)	XX (XXX.X%)
1 – Almost clear	XX (XXX.X%)	XX (XXX.X%)	XX (XXX.X%)
2 – Mild	XX (XXX.X%)	XX (XXX.X%)	XX (XXX.X%)
3 – Mild to moderate	XX (XXX.X%)	XX (XXX.X%)	XX (XXX.X%)
4 – Moderate	XX (XXX.X%)	XX (XXX.X%)	XX (XXX.X%)
5 – Moderate to severe	XX (XXX.X%)	XX (XXX.X%)	XX (XXX.X%)
6 – Severe	XX (XXX.X%)	XX (XXX.X%)	XX (XXX.X%)

Source data: <DATASET> <DATE>
Program: <SAS PROGRAM> <DATE>

Table 14.3.15: PGA – PGA improvement – LOCF (FAS)
Analog to Table 14.3.3 for PGA

Table 14.3.16: PGA – Descriptive statistics – LOCF (VCS)
Analog to Table 14.3.2 for PGA (VCS)

Table 14.3.17: PGA – Frequency counts – LOCF (VCS)
Analog to Table 14.3.14 for VCS

Table 14.3.18: PGA – PGA improvement – LOCF (VCS)
Analog to Table 14.3.3 for PGA (VCS)

Table 14.3.19: BSA [%] – Descriptive statistics – LOCF (FAS)
Analog to Table 14.3.2 for BSA score

Table 14.4.1: PASI – Subgroup: Analysis center – ANCOVA for change from baseline – LOCF (FAS)
Analog to Table 14.3.7 for Subgroups: Analysis centers (pooled): 1; 2; ...; [**<X>**](#).

Table 14.4.2: PASI – Subgroup: Age – ANCOVA for change from baseline – LOCF (FAS)
Analog to Table 14.3.7 for Subgroups: Age: 18 to 40; >40.

Table 14.4.3: PASI – Subgroup: Sex – ANCOVA for change from baseline – LOCF (FAS)
Analog to Table 14.3.7 for Subgroups: Sex: Male; Female.

Table 14.4.4: PASI – Subgroup: BMI – ANCOVA for change from baseline – LOCF (FAS)
Analog to Table 14.3.7 for Subgroups: BMI: Normal (≤ 24.9); Pre-obesity (25.0 - 29.9); Obesity (≥ 30.0).

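### The full-analysis-set tables for both co-primary endpoints are labelled LOCF, although the protocol and SAP text score missing PASI or PGA as failure

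*SAP*

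**What the plan says.** **Text.** Protocol 6.6 sets the rule for the primary success rates: "missing PGA assessments and/or any parts of the PASI assessments will be evaluated as failure to achieve improvement". SAP 3.5.1 repeats it in the same words and then limits the other method: "For descriptive analyses of PASI, PGA and BSA the last observation carried forward (LOCF) principle will be applied", up to the Day 84 visit. It adds: "Follow-up assessments will not be imputed". SAP 3.1 defines LOCF as the last observed value, scheduled or not, "carried forward and used for all directly subsequent and missing scheduled points". The opening of Protocol 6 allows statistical methods to change before database lock if the change is documented in the SAP. SAP 1.3, headed "Modifications from the statistical section in the protocol", is marked not applicable.

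**Shells.** The SAP Appendix has one FAS table for each co-primary endpoint: "Table 14.3.3: PASI – PASI 75 responders – LOCF (FAS" and "Table 14.3.15: PGA – PGA improvement – LOCF (FAS" (both titles cut before the closing bracket). Table 14.3.3 repeats LOCF in its column header, and 14.3.15 is built on the same layout. The Week 12 block holds the Cochran-Mantel-Haenszel p-value, the common odds ratio with its interval and the Breslow-Day test, which is the primary analysis of SAP 3.4.6.2. The table list contains no version that scores missing as failure, and no footnote mentions that rule. The secondary PASI 50 shell (14.3.4) and the per-protocol shells (14.3.9, 14.3.18) carry the same label.

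**The concern.** These shells are where both co-primary results will be reported, and SAP 3.3.1 makes the FAS the primary efficacy set. A programmer working from the shell and one working from SAP 3.5.1 would report different response rates and odds ratios whenever a patient has no Week 12 value and a last value that meets the criterion.

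The planned sensitivity analysis would not expose this. It is the per-protocol analysis on the valid cases set (VCS), and SAP 3.3.1 requires Day 84 PASI and PGA for membership, so at Week 12 the two rules give the same answer there. At stake is which estimate is reported, and whether that is fixed before the blind is broken.

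**Working it through.** **1. The plan's own figure.** Inputs from SAP 2.2: rates 0.674 and 0.40, two-sided alpha 0.10, power 80%. With pooled variance and no continuity correction:

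n = [1.645 × √(2 × 0.537 × 0.463) + 0.842 × √(0.674 × 0.326 + 0.40 × 0.60)]² / 0.274² ≈ 39.9, so 40 per group (power 0.801).

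The stated 40 reproduces, and nothing here disputes it. The same two rates are used below.

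**2. Who is classified differently.**
- *No withdrawal visit.* Protocol 5.5.1 asks for an early termination visit only if possible. A patient attends Week 8 with PGA one point better than baseline and is not seen again. LOCF makes this a Week 12 responder; SAP 3.5.1 makes it a failure.
- *Withdrawal score mapped to Week 8.* When the early termination visit takes place, Protocol 5.5.1 says: "The observations and procedures scheduled for Visit 5 (End of Treatment) should be performed at the Early Termination Visit". SAP 3.5.2 and 3.5.3 then map the scores to a planned visit. Suppose the last planned visit attended was Week 4 and the withdrawal visit is on Day 50. The midpoint of Days 28 and 56 is Day 42, and that of Days 56 and 84 is Day 70, so Day 50 maps to Week 8 and Week 12 stays empty. The rules disagree if the Day 50 score meets the criterion.
- *Withdrawal score mapped to Week 12.* The two rules agree.

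**3. Size of the difference.** With about 50 FAS patients per arm, one reclassified patient moves that arm by 1/50 = 2.0 points. The documents give no missing share, so the following is an illustration. Assumptions: the SAP 2.2 rates p hold among patients with Week 12 data, a share d of each arm has none, and the carried value is a response at k times that arm's own rate, with k from 0.25 to 1.

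Failure rate = p(1 − d). LOCF rate = p(1 − d) + k·p·d.

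At d = 0.20:
- Failure: 0.674 × 0.80 = 0.539 and 0.40 × 0.80 = 0.320, odds ratio 2.49.
- LOCF, k = 0.25: 0.5392 + 0.0337 = 0.573 and 0.320 + 0.020 = 0.340, odds ratio 2.60.
- LOCF, k = 1: 0.674 and 0.400, odds ratio 3.10.

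| d, equal in both arms | Failure: active vs placebo | Failure: difference, OR | LOCF: difference, OR |
|---|---|---|---|
| 5% | 64.0% vs 38.0% | 26.0 points, 2.90 | 26.4 to 27.4 points, 2.95 to 3.10 |
| 10% | 60.7% vs 36.0% | 24.7 points, 2.74 | 25.3 to 27.4 points, 2.82 to 3.10 |
| 20% | 53.9% vs 32.0% | 21.9 points, 2.49 | 23.3 to 27.4 points, 2.60 to 3.10 |

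Odds ratios are unstratified.

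**4. Direction.** LOCF cannot lower an arm's rate relative to failure scoring. The difference between arms changes by cA·dA − cP·dP, where c is the share of missing patients whose carried value is a response. With c = k·p, the change is negative only if dA/dP < 0.40/0.674 = 0.593. The odds ratio can also move either way (k from 0.5 to 1):
- 10% missing on active, 30% on placebo: 3.96 under failure, 3.46 down to 3.10 under LOCF.
- 30% on active, 10% on placebo: 1.59 under failure, 2.19 up to 3.10 under LOCF.

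**The case against.** The strongest reply is that there is one rule and a stray label. The protocol and SAP state failure scoring in matching words, no sentence in the SAP body applies LOCF to success rates, and SAP 1.3 declares no change. The label also stands over the Week 16 rows, where imputation is ruled out, and on the VCS shells, where Day 84 data are required. That looks like a carried-over template. This stands as evidence of intent, so a reader who infers that the SAP has adopted LOCF for the primary analysis, or offers two rules of equal rank, goes too far. It does not remove the label. The time-to-PASI shells (14.3.5, 14.3.6) omit LOCF, so it was not put on every efficacy table. SAP 3.4.6.1 calls the whole evaluation descriptive, which lets a programmer read LOCF for descriptive analyses as covering responder tables.

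A second reply is that the illustration is generous, and that is fair. The 20% case borrows the whole 150-to-120 allowance, (150 − 120)/150. The documents do not define evaluable. If it means the VCS, the allowance also covers prohibited medication and low dosing, which leave Week 12 data in place. Patients with no post-baseline assessment leave the FAS altogether. SAP 3.5.2 can also be read as sending any withdrawal score after an attended Week 8 visit to Week 12, which would shrink the affected group. A carried PASI 75 response is a higher bar than a one-point PGA change. At 20% missing, the failure odds ratio of 2.49 has an approximate 95% interval of 1.1 to 5.6 (unstratified, 50 per arm), and the LOCF values lie inside it.

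A third reply concerns the denominator. SAP 3.4.6.2 bases percentages on non-missing cases only where nothing else is stated, and 3.5.1 does state otherwise for the primary success rates. The Week 12 co-primary denominator is therefore settled by the text; a footnote would only make it visible.

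**Conclusion.** The mismatch is real and should be corrected before unblinding. Programmed as labelled, 14.3.3 and 14.3.15 would break the rule in Protocol 6.6 and SAP 3.5.1 for every FAS patient with no Week 12 value after visit mapping whose last value meets the criterion. The effect is 2 points per such patient with 50 per arm. In the equal-missingness illustration the odds ratio goes from 2.90 to between 2.95 and 3.10 at 5% missing, and from 2.49 to between 2.60 and 3.10 at 20%, which is an upper-end case. The missing shares and carry-forward rates are assumptions.

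Three stronger conclusions are tempting and not supported:
- *That LOCF favours the drug.* It raises arm rates, but the contrast depends on missingness by arm, which is unknown.
- *That an error rate is at risk.* The trial postulates no formal hypotheses and its p-values are descriptive.
- *That the Week 12 per-protocol results are wrong.* The VCS requires Day 84 PASI and PGA, so the label has no effect there.

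Severity: should-fix.

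**What to change.** Before unblinding:
1. Retitle 14.3.3, 14.3.15 and 14.3.4, and for consistency 14.3.9 and 14.3.18, as 'missing = failure' in both title and column header. Program them that way, with all patients of the analysis set in the denominator through Week 12, and say so in a footnote.
2. Take the LOCF label off the Week 16 rows and state how a missing Week 16 value is handled: as failure, which SAP 3.4.6.2 implies by evaluating follow-up like the primary endpoints, or excluded with its own N.
3. Keep any LOCF responder table only as a separately named sensitivity analysis.

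Cost: five shell titles and headers, one programming flag, one footnote and one sentence in the SAP. Reported rates fall only if the programs would otherwise have followed the label. In the 20% illustration that is 3.4 to 13.5 points on active (0.25 to 1 × 0.674 × 0.20) and 2.0 to 8.0 points on placebo (0.25 to 1 × 0.40 × 0.20).
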